Additionally, participants will receive treatment over any tender spots reported in the hips, knees, shoulder, or elbows. Total treatment time to the spine will range from 12-14 minutes, depending on the size of the subject. Total treatment time to extremity joints will not exceed two minutes per site, so that the total treatment time to the spine and extremities will not exceed 30 minutes. All treatment for the LLLT group will be delivered at an intensity of 42 watts. The treatment will be applied via a non-contact method, with the laser applicator held 15 inches above the participant's skin. Sham treatment will be delivered via the same protocol in terms of time, application, and areas of treatment as stated above, except the laser unit will not discharge any photonic energy. Intervention will take place in the therapy room at the Health Professions Physical Therapy Clinic, which is appropriately equipped for laser administration. Application of therapeutic laser will be completed by licensed physical therapists who have completed safety training for therapeutic laser application including appropriate use of safety eyewear, room access, laser signage for laser use, and patient monitoring.

The following outcome measures will be collected at baseline: (1)Standardized SF-36 questionnaire; (2) Symptom Impact Questionnaire; (3) Current analgesic medication usage; (4) Pressure-pain threshold testing over tender points; and (5) Spinal ROM with an inclinometer and accelerometer. Outcome measures (2) and (3) will be re-assessed during the treatment phase at the end of weeks 1, 2 and 3. At 1 week and 1 month after the last laser/sham treatment session, all baseline assessments will be repeated, in addition to a global rating of change scale (-7= very harmful, 0=

neutral, +7 = very helpful). Any patient who reports any harm from the laser/sham treatments on the helpfulness scale will be queried for specific harm details. Participants randomized to Sham will have the option of receiving LLLT treatments after they complete their study enrollment.

5. Sub-Study Procedures:

Not applicable for this study.

6. Criteria for Inclusion of Subjects:

- 1) 18-80 years old
- 2) Pre-existing medical conditions are under stable control
- 3) Diagnosis of fibromyalgia by standard criteria (e.g., pain in all four body quadrants for over 3 months, 11 of 18 tender points, bilaterally in the cervical and upper thoracic back areas, and chronic fatigue)

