Evaluation of the a-priori sample size was calculated utilizing a power analysis. This analysis was based on the primary outcome measure (pain) being a continuous response variable. Data from previous published research on the projects primary intervention conducted over longer periods of treatment time supports an effect size of 0.4 on the impact of Class III light therapy techniques. Power calculations for the current project were based on mean differences between two dependent groups (matched pairs), power (1- β probability) = 0.80, α error probability = 0.05, and effect size of 0.4 (GPower ver. 3.1). These parameters resulted in a total sample size calculation of 52 to reject the null hypothesis. Accounting for a dropout rate of no more than 15%, a final sample size of 60 was selected. Dependent variables will be evaluated with non-parametric analysis for reports of patient well-being, while repeated measure ANOVAs will be utilized for changes of significance over time in pain, quality of life, function, ROM, and pressure-pain threshold. Significance will be set at p<0.05.

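### Section 14 gives the baseline score no covariate role, so the laser-sham comparison appears to rest on raw change from baseline and gives up precision that is free to recover

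*Combined protocol and SAP*

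**What the plan says.** The whole analysis plan for the continuous outcomes is one clause in Section 14 (Biostatistics): "repeated measure ANOVAs will be utilized for changes of significance over time in pain, quality of life, function, ROM, and pressure-pain threshold". It names no covariate and no between-group factor. It does not say whether the laser effect is to be read from the group main effect or from the group-by-time interaction, or whether baseline is one of the time levels.

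Section 4 (Study Procedures) has participants complete the baseline assessments after consent and then be randomised. It lists the measures under "The following outcome measures will be collected at baseline": SF-36, Symptom Impact Questionnaire, analgesic use, pressure-pain threshold and spinal ROM. At 1 week and 1 month after the last session "all baseline assessments will be repeated". The Symptom Impact Questionnaire and analgesic use are also taken at the end of treatment weeks 1, 2 and 3. The questionnaire therefore has six occasions (baseline plus five), and SF-36, pressure-pain threshold and ROM have three (baseline plus two).

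**The concern.** A repeated-measures ANOVA of change over time, with no covariate, needs a starting level. For the outcomes with only two post-treatment occasions, change from before treatment can be seen only if baseline is itself a level of time. On that reading the group-by-time comparison works on raw change from baseline. Subtracting the whole baseline score corrects for it fully even when the within-patient correlation is below 1, and so adds noise that a regression adjustment would not.

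The trial is small: 50 participants in Section 3, 60 in Section 14. The baseline values are already being collected. Any precision lost here is lost for no saving, and if the role of baseline is left open it could be settled after the results are known.

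**Working it through.** **The plan's own figure.** Section 14 bases its sample size on "mean differences between two dependent groups (matched pairs", with "α error probability = 0.05", "power (1- β probability) = 0.80" and a standardised effect of 0.4. A two-sided paired t-test with the noncentral t gives power 0.7999 at n = 51 and 0.808 at n = 52, so n = 52. This agrees with the plan: "These parameters resulted in a total sample size calculation of 52 to reject the null hypothesis". The figure reproduces, but it comes from a paired test with no between-arm contrast and no baseline adjustment, so it neither supports nor refutes this point.

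**Inputs for the comparison.**
- From the documents: 52/2 = 26 per arm; m = 5 or m = 2 post-baseline visits (Section 4); alpha 0.05, taken as two-sided because only that reproduces 52.
- Assumed, because the documents give nothing: outcome SD 1 at each occasion; the same correlation r between any two occasions, from 0.3 to 0.8; a laser effect of 0.4 raw SD at every post-baseline visit.

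**Formulas (variance per patient).**
- Change contrast, mean of post-baseline visits minus baseline: V_chg = (1 − r)(1 + 1/m).
- Baseline-adjusted mean of post-baseline visits: V_adj = [1 + (m − 1)r]/m − r².
- Noncentrality = (26/2) × 0.4² / V = 2.08/V, on 1 and 50 df (change) or 1 and 49 df (adjusted).

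**Example at r = 0.6.**
- Six occasions: V_chg = 0.4 × 1.2 = 0.48; V_adj = 3.4/5 − 0.36 = 0.32; ratio 0.67. Noncentrality 4.33 against 6.50.
- Three occasions: V_chg = 0.4 × 1.5 = 0.60; V_adj = 1.6/2 − 0.36 = 0.44; ratio 0.73. Noncentrality 3.47 against 4.73.

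| r | Occasions | V_chg | V_adj | Variance saved | Power, change | Power, adjusted |
|---|---|---|---|---|---|---|
| 0.3 | 6 | 0.840 | 0.350 | 58% | 0.339 | 0.666 |
| 0.5 | 6 | 0.600 | 0.350 | 42% | 0.447 | 0.666 |
| 0.6 | 6 | 0.480 | 0.320 | 33% | 0.533 | 0.705 |
| 0.7 | 6 | 0.360 | 0.270 | 25% | 0.654 | 0.777 |
| 0.8 | 6 | 0.240 | 0.200 | 17% | 0.823 | 0.885 |
| 0.3 | 3 | 1.050 | 0.560 | 47% | 0.282 | 0.472 |
| 0.5 | 3 | 0.750 | 0.500 | 33% | 0.372 | 0.516 |
| 0.6 | 3 | 0.600 | 0.440 | 27% | 0.447 | 0.568 |
| 0.7 | 3 | 0.450 | 0.360 | 20% | 0.559 | 0.654 |
| 0.8 | 3 | 0.300 | 0.260 | 13% | 0.733 | 0.792 |

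The variance ratio does not depend on n. At 25 and 30 per arm the adjusted analysis is again the more powerful at every correlation tried. These figures leave out the small cost of estimating the slope, on average a factor 1 + 1/(52 − 4) = 1.02 on V_adj. In the least favourable row that moves the ratio from 0.867 to about 0.885 and does not change the direction.

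**Other tests that Section 14 would allow (r = 0.6, 26 per arm).**
- Omnibus group-by-time test, on 5 or 2 df: power 0.31 (six occasions) or 0.36 (three).
- Group main effect averaged over all occasions including baseline: the effect shrinks to 5/6 × 0.4 = 0.33 SD or 2/3 × 0.4 = 0.27 SD, with power 0.30 or 0.20.

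**The case against.** The strongest reply is that Section 14 is silent rather than wrong, and that randomisation makes an unadjusted comparison of change valid. Both parts stand. This is a loss of efficiency, not a bias, and baseline as a time level is inferred from the wording.

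A reader might also infer more than the documents support:

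- *That the plan's analysis dilutes the laser effect.* Only the group main effect is diluted. Section 14 does not name that test, and its emphasis on change over time points to group-by-time, where the post-minus-baseline contrast estimates the full effect.
- *That a chance baseline gap is counted as treatment effect.* This too belongs to the main effect. A change score subtracts the gap and over-corrects: at r = 0.6 a gap of 0.4 SD moves the estimate by (1 − 0.6) × 0.4 = 0.16 SD in the opposite direction.
- *That the covariate takes six-occasion power from 0.31 to 0.70.* Moving from the 5-df omnibus test to a 1-df contrast already gives 0.53. That is 0.22 of the 0.39 gain, more than half; only the step from 0.53 to 0.70 is due to adjustment.
- *That 0.4 raw SD is the planned effect.* The plan's 0.4 comes from a paired calculation and is in SDs of differences. At r = 0.6 it would equal 0.4 × √(2 × 0.4) = 0.36 raw SD, and at r = 0.7, 0.31.

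Three limits also stand. The gain shrinks as r rises. A full effect at every visit, including the end of week 1 after three of nine sessions, favours averaging. And Section 14's primary outcome, pain, is tied to no instrument, so either six or three occasions may apply to it. None of these reverses the like-for-like comparison.

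**Conclusion.** The point holds as a matter of precision. The plan collects a pre-randomisation value of every continuous outcome and assigns it no covariate role. On the natural reading it compares raw change, which is valid but less efficient than adjustment at every correlation examined. The loss is material at moderate correlation and modest at 0.8.

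The variance savings rest on the assumed exchangeable correlation. The power figures rest also on the assumed 0.4 raw-SD effect, constant over the post-baseline visits, and on 26 per arm. Naming a laser-sham contrast would not by itself settle the matter, because the change contrast used as comparator already supposes that one has been named.

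**What to change.** In Section 14, replace the repeated-measures ANOVA clause with a statement along these lines: each continuous outcome will be compared between laser and sham in a model of the post-baseline visits only, with that outcome's baseline value as a covariate. The model will be either ANCOVA on the mean of the post-baseline visits or a repeated-measures model with baseline and baseline-by-visit terms. One prespecified adjusted mean difference will be reported with its 95% CI.

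The paragraph should say which visits enter that difference, since the gains above are for the mean of all post-baseline visits. ANCOVA at a single visit has power 0.42 at r = 0.6 (noncentrality 2.08/0.64 = 3.25). That is still above change at the same single visit (2.08/0.80 = 2.60, power 0.35), but below the 0.53 of the averaged six-occasion change contrast.

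The cost is one paragraph and one degree of freedom, slightly more with baseline-by-visit terms. No new data, visits or patients are needed.
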